The primary outcome is the count of patients who received the composite outcome of any of the following: naloxone dispensing [prescription, free kit from clinic, or order for home kit], medication assisted treatment [buprenorphine, methadone, naltrexone, acamprosate, gabapentin, disulfiram], addiction consult, referral to outpatient treatment, brief intervention/motivational interviewing for substance misuse. Each component will be indicated separately in the flowsheet for the encounter, along with the type of SUIT team involvement: formal consultation, curbside consultation, or supporting other service. The design is an interrupted time-series prospective observational study. [Time Frame: 30 months]

The secondary outcome is all-cause re-hospitalizations following 6-months from the Index hospital encounter. We will compare healthcare utilization outcomes in all patients between manual screen period and automated screen period controlling for all patient demographic and clinical characteristics. [Time Frame: 24 months of evaluation with 6 months follow-up for rehospitalization] Further exploratory outcomes include analyzing each component of the primary outcome separately: naloxone dispensing, medication assisted treatment, addiction consult, referral to outpatient treatment, brief intervention/motivational interviewing for substance misuse.

Analysis Plan:

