Overall approach: Demographic and clinical characteristics between the manual and automated screen periods will be examined using bivariate statistics. We will also perform descriptive analysis to examine the proportion of hospitalized patients with substance misuse who received any component of the composite outcome (naloxone dispensing, medication-assisted treatment, addiction consult, referral to outpatient treatment, brief intervention/motivational interviewing for substance misuse) within each month of the study period, and we will plot these proportions using mixed-effects logistic regression, with time (month of observation) modeled using restricted cubic splines. The primary analysis for aim 1 will consist of an interrupted time series approach utilizing autoregressive integrated moving average (ARIMA) models to determine the effect of the automated screener to the manual screen for this outcome. ARIMA models are preferable to alternatives such as segmented regression which may inadequately control for seasonality and autocorrelation in time series data. We will also perform sensitivity analyses to confirm the results of aim 1 using generalized linear mixed-effects models (GLMM) that include random intercepts to account for multiple index encounters over the follow-up time period and adjust for important patient demographics and clinical characteristics including: age, sex, race/ethnicity, insurance status, diagnosis, and comorbidities. GLMMs will also be used to analyze secondary endpoints.

Specific aim 1: First, we will plot the counts of hospitalized patients who received any component of the composite outcome to examine seasonality, trends, and outlying values. A transformation will be applied to stabilize the variance over time if data are heteroscedastic. Differencing will be applied to induce stationarity, such as a difference to account for linear trend ($d=1$, degree of non-seasonal differencing) and autocorrelation functions (ACF) will be plotted to verify stationarity. After differencing,

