ACFs and partial ACFs will be used to determine the orders of autoregression (AR) or moving average (MA) that will correct for the remaining autocorrelation. We hypothesize that the intervention will promote a step change (binary indicator for a level shift when intervention begins) and possibly a ramp effect (variable takes the value of 0 before the intervention and increases by 1 for each month following the beginning of the intervention). Fit statistics (AIC, BIC) and residual analysis (Ljung-Box test for white noise) will be used to identify a parsimonious and appropriate model based on AR/MA orders, differencing assumptions, and parameters for intervention impact (step, pulse, or ramp).

Specific aim 2: The number of hospitalizations in the 6 months following the index encounter will be regressed on time period of index hospitalization (manual screen or automated screen) and patient demographic and clinical characteristics using mixed-effects Poisson regression models. GLMMs with appropriate link and distributions specified will consider other follow-up utilization outcomes (e.g., costs, any encounter).

Power analysis:

A simulation study was designed to examine potential step effects in a non-inferiority design. In 2020, there were 95 ± 10 addiction consults per month and an autocorrelation AR(1) of $\phi=0.4$. Additionally, we performed silent testing of the automated screener in 2020 where it detected ~ 70 additional cases of substance misuse per month that did not receive consults by the usual care approach. We propose that a non-inferiority margin of 15 consults is acceptable and a step effect of 20 is a feasible goal with the implementation of automated screening. Assuming a similar consult rate of 95 ± 10 per month in this study's pre-period (July 2022-June 2023) and $\phi=0.4$, we have 80% power to detect a step effect of +20, resulting in 115 ± 10 consults per month in the post-period (July 2023-June 2024).

Data Elements:

RUSH EHR

The following electronic health record data elements will be included in the data sets used for analysis. Most data will be obtained through direct extraction of EPIC; however, some data may be computed from EHR data and obtained through the Rush Clinical Research Analytics team or transformed from EHR data by the research team (NLP mapped concepts from the text):

- MRN
- Address with Geocoding
- Census Tract Identifiers
- Encounter ID and type

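### The only margin (15 per month) and power (80%) are for addiction consults, not the composite primary outcome, and Specific aim 1 neither fixes the effect to be tested nor compares it with the margin

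*Combined protocol and SAP*

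**What the plan says.** All references are to the combined protocol and SAP.

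- **Study Outcomes:** "The primary outcome is the count of patients who received the composite outcome of any of the following". Five components follow: naloxone dispensing, medication-assisted treatment, addiction consult, outpatient referral, and brief intervention or motivational interviewing. Then: "Further exploratory outcomes include analyzing each component of the primary outcome separately". Addiction consult is one of the components listed there.
- **Analysis Plan, Overall approach:** the primary analysis uses ARIMA "models to determine the effect of the automated screener to the manual screen for this outcome", where the outcome just described is the composite.
- **Specific aim 1:** the series is the composite count. "A transformation will be applied to stabilize the variance over time if data are heteroscedastic". The authors expect a step change "and possibly a ramp effect". Then: "Fit statistics (AIC, BIC) and residual analysis (Ljung-Box test for white noise) will be used to identify a parsimonious and appropriate model", with the choice covering AR/MA orders, differencing and "parameters for intervention impact (step, pulse, or ramp").
- **Power analysis:** 95 ± 10 addiction consults per month in 2020, AR(1) with phi 0.4, a non-inferiority margin of 15 consults, a target step of +20, and "we have 80% power to detect a step effect of +20".
- **Opening summary, before Scientific Review:** the classifier is hypothesised to be non-inferior to the manual screen, and to lead to as many or more patients with consults, medication-assisted treatment and referrals.

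**The concern.** There are two linked problems.

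**The powered outcome is not the primary outcome.** Every planning figure is for consults. The composite also counts patients who had only naloxone, medication, a referral or a brief intervention, so its monthly level, spread and autocorrelation may differ. A loss of 15 is 15/95 = 15.8% of the consult baseline. What share of the composite baseline it would be is unknown, and whether a loss of that size is tolerable on the composite is not argued.

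**Non-inferiority is declared but has no test.** An analyst who follows Specific aim 1 obtains an estimate, but no rule for concluding on the stated hypothesis. The estimate is not fixed either. Its shape, its differencing and possibly its scale are settled after looking at the data, and the same 24 points then supply the inference. The same series could therefore meet or miss the margin depending on the model chosen, and ordinary intervals computed after such a choice do not have their nominal coverage.

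**Working it through.** **Inputs.** From Power analysis: SD 10, phi 0.4, margin 15, target step +20. From Trial Setting and Participants: 12 months before and 12 after. Not stated: alpha, sidedness, the null tested, the simulated model, and whether ±10 is the marginal SD or the innovation SD. I use both readings (innovation SD 10 gives a marginal SD of 10/√(1 - 0.16) = 10.91) and two alpha levels.

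**Standard error.** With phi known, the variance of the step is the step element of σ²(X′R⁻¹X)⁻¹, where R has entries 0.4^|i-j| over 24 months and X holds the intercept and model terms.

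**Formulas.**
- Power for +20 against zero: Φ(20/SE - z)
- Non-inferiority power at a true step of 0: Φ(15/SE - z)
- Estimate needed to clear the margin: -15 + z·SE

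Here z = 1.96 for two-sided 5% or one-sided 2.5%, and 1.645 for one-sided 5%.

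Worked line (step only, marginal SD, z = 1.96): SE 5.60. Then 20/5.60 - 1.96 = 1.61, giving 94.7%; 15/5.60 - 1.96 = 0.72, giving 76.4%; and -15 + 1.96 × 5.60 = -4.0.

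Pairs below are marginal / innovation SD.

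| Model | SE of step | +20 vs 0, two-sided 5% | +20 vs 0, one-sided 5% | Non-inf. at 0, one-sided 2.5% | Non-inf. at 0, one-sided 5% | Estimate needed (2.5%) |
|---|---|---|---|---|---|---|
| Step only | 5.60 / 6.11 | 94.7 / 90.6% | 97.3 / 94.8% | 76.4 / 69.0% | 84.9 / 79.1% | -4.0 / -3.0 |
| Step + ramp coded 0 to 11 | 7.67 / 8.37 | 74.1 / 66.6% | 83.2 / 77.2% | 49.8 / 43.4% | 62.2 / 55.9% | 0.0 / +1.4 |
| Step + ramp coded 1 to 12 | 8.43 / 9.20 | 66.0 / 58.5% | 76.6 / 70.2% | 42.8 / 37.1% | 55.3 / 49.4% | +1.5 / +3.0 |
| Trend + step + slope change | 9.48 / 10.34 | 56.0 / 49.0% | 67.9 / 61.4% | 35.3 / 30.5% | 47.5 / 42.3% | +3.6 / +5.3 |

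**The plan's 80%.** It lies inside the range for +20 against zero, and the one-sided 5% entries for step + ramp coded 0 to 11 bracket it (83.2 / 77.2%). No variant reproduces it to within two points. Non-inferiority power at a true +20, Φ(35/SE - 1.96), is 92% or more in every row. Without a stated null, alpha and model, the 80% can be neither confirmed nor refuted.

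**Interval method.** In simulated series with a true step of -15, an AR(1) regression fitted by maximum likelihood to 24 points with a 1.96·SE interval wrongly clears the margin about 8% of the time (step only) to 10% (trend + step + slope), against a nominal 2.5%.

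**Selection (illustration).** With no true effect, I let AIC or BIC choose among step, ramp, pulse and step + ramp, holding AR(1) errors fixed. The chosen model showed a significant intervention term (two-sided 5%) in about 35 to 39% of series, against 16 to 17% for a fixed step fitted in the same way. The candidate list has no no-intervention model; adding one would change the figure.

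**Composite.** The documents give no composite mean, SD, phi or margin. Purely as assumed values, with margin 15, phi 0.4 and the step-only model: a composite SD of 15 (SE 8.40) gives non-inferiority power at a true step of 0 of Φ(15/8.40 - 1.96), about 43%; an SD of 20 (SE 11.20) gives about 27%.

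**The case against.** The strongest reply is that nothing here is a strict contradiction. Consult is a component of the composite, and the opening hypothesis names consults, so a consult series is a plausible planning proxy. A step is the expected shape, and the Power analysis section speaks of non-inferiority and a margin, so a comparison of the step with -15 is implied. All of this stands. It makes the point a mismatch of outcomes plus an unwritten test. It does not supply the proxy argument, the decision rule or a fixed effect measure.

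The documents do not support four stronger readings that a reader might infer:

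- **That a non-significant step will be taken as non-inferior.** The plan never says so, and its margin points the other way. Error rates under that reading would test a rule the plan does not state.
- **That a model without a step leaves nothing to compare with the margin.** A ramp coefficient multiplied by months is a difference in patients per month (mean 6.5 × slope with coding 1 to 12), and a transformed effect can be converted back through counterfactual predictions. What is missing is a statement of which quantity counts. How often selection drops the step when nothing has changed mostly reflects near-equal choice among labels.
- **That the 80% is an arithmetic error.** It cannot be tied to any stated test.
- **That the table sizes the problem for the composite.** It uses consult inputs only and shows how much the model choice matters.

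**Conclusion.** The point holds as a mismatch between the planned and the powered outcome, joined to a data-driven choice of effect with no margin test. The mismatch and the missing rule follow from the text alone. The size of the second part, on the consult inputs with phi 0.4 treated as known, is the spread in the table: the step SE runs from 5.60 to 10.34, and the estimate that would establish non-inferiority moves by about 9 patients per month (from -4.0 to +5.3) on a margin of 15. Relaxing to one-sided 5% raises every power figure but leaves a wide spread: 85% down to 42% for non-inferiority with no true change. The results assume AR(1) errors, 12 + 12 monthly points and no differencing. Nothing quantitative can be said about the composite until its inputs are given.

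**What to change.** 1. **Specific aim 1, effect and rule.** Pre-specify one intervention term and effect measure for the composite in patients per month, untransformed: for example the step, or the mean post-period difference from the counterfactual. Fix the rules for differencing and transformation, and the ramp coding if a ramp is kept. Make other shapes sensitivity analyses. Suggested wording: *Non-inferiority is concluded only if the lower confidence limit for this effect on the composite count exceeds minus the margin.*
2. **Interval.** Choose the interval method and level by simulation on 24 points before the outcome series is examined. The plain 1.96·SE interval should not be adopted by default, given the 8 to 10% error above.
3. **Margin and power.** Restate and justify the margin for the composite. Replace the 80% sentence with the simulated power of this rule at true steps of 0 and +20, and its error at a step equal to minus the margin. Name null, alpha, model and inputs. Take the composite's monthly mean, SD and phi from available EHR data, or give a stated range. Failing that, label the consult figures as a planning proxy only.

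**Cost.** SAP wording, a margin justification and a rerun simulation. The interval will be wider and the stated power may be less favourable. The primary outcome is unchanged, and no extra patients or months are needed.

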The COVID pandemic has surfaced major gaps in healthcare, including addiction disease. In 2020, overdose deaths soared to an all-time high with a record 93,000 deaths nationwide during the pandemic year. Substance misuse ranks second among principal diagnoses for unplanned 7-day hospital readmission rates. Despite the availability of Screening, Brief Intervention, and Referral to Treatment (SBIRT) interventions, substance misuse is not part of the admission routine and only a minority of patients are screened for substance misuse in the hospital setting, especially during the COVID pandemic. This is particularly problematic, since among hospitalized inpatients, the prevalence of substance misuse is estimated to be as high as 25%, greater than either the general population or outpatient setting. Practical screening methods tailored for the hospital settings are needed.

Routinely collected data in the electronic health record (EHR) may be leveraged to identify cases of substance misuse. Patients are more likely to disclose substance use to their hospital primary care team than to designated screeners who are not part of the care team. The admission notes and social history sections of notes written by the provider teams frequently contain details about substance use but are rarely accessed for surveillance or screening programs. Computational methods of natural language processing (NLP) can derive discrete representations of clinical notes, from which machine learning can predict substance misuse better than rule-based approaches.

We previously published and made publicly available a substance misuse classifier using NLP and machine learning from the clinical notes. In hospitalized patients, our convolutional neural network (CNN) outperformed a rule-based approach and other machine learning methods. Our CNN substance misuse classifier had greater than 80% sensitivity and specificity, and our results showed that clinical notes from the hospitalization can be used to identify substance misuse and serve as an alternative to manual screening by staff. The trained model comprised of 15,651 medical concepts from 63,301 notes fed into the CNN. The top positive features included terms such as 'heroin', 'opiates', 'drug abuse', and 'polysubstance abuse'.

RESEARCH PLAN:

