In this study, the aim is to prospectively implement our NLP substance misuse classifier to examine its effectiveness in augmenting current practice that features physician referrals in hospitalized adult patients at Rush University Medical Center (RUMC).

STAFF

All work involving patient data will be performed at Rush and Rush staff will gain access to the Rush servers with approved credentialing and authentication by Rush IT. No data will be accessible to external investigators without a fully executed data use agreement and/or IRB approval / SMART IRB reliance agreement.

TRIAL SETTING AND PARTICIPANTS

This pragmatic, quasi-experimental (pre-post) study will be implemented at Rush University Medical Center across the surgical and medical wards. The study will target all adult hospitalized patients over a 24-month period (12 months of manual screen and 12 months under implementation of the NLP tool) and an additional 6-month follow-up for secondary outcomes. Currently, SUIT performs screening for patients identified from physician referrals between 8am-6pm and Monday-Friday and uses Epic (Epic Systems Corporation, Verona, Wisconsin) EHR.

METHODS AND MATERIAL

Overview:

We will use a quasi-experimental, interrupted time series (ITS) design to evaluate the longitudinal effects of the automated screening classifier compared to the manual screen approach at Rush. ITS offers several advantages in making use of our longitudinal data. Our analysis will model the trend in the outcome before the implementation of the automated screen, the change in the outcome that can be attributed to the automated screen and the difference between the slopes in the pre-period versus post-period. It is anticipated that no other interventions that may impact the study outcome will occur during the study period.

A comparison cohort from the manual screen period will extend from August 1, 2022 to July 31st, 2024. The day of switching on the automated screen will mark the start of the intervention period on August 1, 2023 and extend through July 31, 2024. This provides a 30-month total study period (12 months manual screening, and 12 months automated screen, and 6 months additional follow-up for secondary outcomes).

Approach:

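### The only power figure, 80% for a step of +20, is not tied to the non-inferiority test or to the trend-adjusted analysis, and the natural readings give other values

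*Combined protocol and SAP*

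**What the plan says.** All references are to the combined protocol and SAP.

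- The opening summary hypothesizes that the classifier is non-inferior to the manual screen.
- Power analysis: "A simulation study was designed to examine potential step effects in a non-inferiority design". The planning data follow: "In 2020, there were 95 ± 10 addiction consults per month", with AR(1) autocorrelation of 0.4. Then come the margin, "We propose that a non-inferiority margin of 15 consults is acceptable", and the result, "we have 80% power to detect a step effect of +20". No null hypothesis, alpha, sidedness or fitted model is given, and the text does not say whether the 10 is the marginal SD of the monthly counts or the SD of the AR(1) innovations.
- Methods and Material, Overview: "Our analysis will model the trend in the outcome before the implementation of the automated screen", together with the change at switch-on and the difference in slopes between the periods.
- Analysis Plan, Overall approach and Specific aim 1: the primary analysis is ARIMA. First differencing is an example of how linear trend may be handled. A step is hypothesized and a ramp is possible. Orders, differencing and the form of the intervention effect are chosen from fit statistics and residual checks.

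This is the only power statement in the documents. It concerns addiction consults, which are one component of the composite primary outcome. That difference is a separate matter.

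**The concern.** Read plainly, power to detect +20 means power against a null of zero, and the margin of 15 does not enter that calculation. A non-inferiority test asks whether −15 can be excluded. Its power depends on the assumed true step: the distance from the null is 35 if the true step is +20 and 15 if the screens are equal. The model matters as much as the null, because estimating a pre-period trend from 12 monthly points greatly widens the standard error of the step.

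The sentence fixes neither the null nor the model. At stake is whether 12 + 12 months can support the stated hypothesis. If the screens perform equally and trend is modelled, an inconclusive result is more likely than not, and nothing in the plan tells the reader so.

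**Working it through.** **Inputs.** From the Power analysis: SD 10, AR(1) 0.4, step +20, margin 15. From Trial Setting and Overview: 12 months before and 12 after. Assumed because unstated: one-sided alpha of 0.025 or 0.05, and SD 10 read either as marginal or as innovation. On the innovation reading the marginal SD is 10/√(1 − 0.4²) = 10.91.

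**The plan's own figure.** It has no unique reproduction, since null, alpha, model and SD type are missing. With independent months and SD 10, SE = 10 × √(2/12) = 4.08, and power for +20 is Φ(20/4.08 − 1.96) = 99.8%. Autocorrelation has to be brought in.

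**Formula.** SE² = SD² × the step element of (X′R⁻¹X)⁻¹, with R having entries 0.4^|i−j| over 24 months and the autocorrelation taken as known. Power = Φ(distance/SE − z), with z = 1.96 or 1.645. The distance is 20 (+20 against zero), 35 (non-inferiority, true +20) or 15 (non-inferiority, true 0).

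Example, step only with marginal SD: 20/5.60 − 1.96 = 1.61, giving 94.7%. With trend: 20/9.48 − 1.96 = 0.15, giving 56.0%.

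Power in %, at one-sided 0.025 / 0.05:

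| Model | SD 10 is | SE | +20 vs 0 | NI, true +20 | NI, true 0 |
|---|---|---|---|---|---|
| Step only | marginal | 5.60 | 94.7 / 97.3 | 100 / 100 | 76.4 / 85.0 |
| Step only | innovation | 6.11 | 90.6 / 94.8 | 100 / 100 | 69.0 / 79.1 |
| Pre-trend + step + ramp | marginal | 9.48 | 56.0 / 67.9 | 95.8 / 98.0 | 35.3 / 47.5 |
| Pre-trend + step + ramp | innovation | 10.34 | 49.0 / 61.4 | 92.3 / 95.9 | 30.5 / 42.3 |

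Dropping the ramp but keeping the pre-trend moves these by at most 0.3 points (SE 9.44 and 10.30).

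**Settings that do come near 80% for a true +20.**

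1. Once-differenced ARIMA(0,1,0) with drift, innovation SD 10, null −15, one-sided 0.025. The SE is about 12.5, and 35/12.5 − 1.96 = 0.84, giving 79.9% (82.1% when simulated with estimated variance). At true 0 the same setting gives 15/12.5 − 1.96 = −0.76, or 22%.
2. Step plus ramp with no pre-trend, +20 against zero, one-sided 0.05: 83.2% (marginal SD) or 77.2% (innovation SD) if the ramp is 0 in the first post-period month. If it starts at 1, 76.6% or 70.2%.
3. Fits with estimated autocorrelation, simulated, +20 against zero. An AR(1) model with trend, step and ramp gives 79.7% at nominal one-sided 0.05 (marginal SD), but its actual one-sided error is about 14%. A once-differenced moving-average fit with a step and no drift gives 82.1% (marginal) or 78.1% (innovation) at nominal 0.025, with actual error of about 9%.

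Across simulated once-differenced fits with drift, power runs from 40% to 79% for +20 against zero, and from 81% to 98% for non-inferiority at true +20.

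**The case against.** The strongest reply is that the plan's primary method is ARIMA, with differencing offered as a way to handle trend, and that setting 1 is both a non-inferiority test and trend-adjusted. The wording about detecting +20 could be loose language for excluding −15 when the truth is +20. This stands to the extent that a reader who infers that the 80% is simply wrong goes further than the documents allow: they do not exclude that model or that null. But it does not rescue the sentence. The model fits a random walk to data that the plan assumes are AR(1) with 0.4. The differenced series then has lag-1 autocorrelation of −(1 − 0.4)/2 = −0.3, which Specific aim 1 says would be corrected.

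The reply can add that powering non-inferiority under an expected benefit is legitimate, given that the opening summary expects at least as many treated patients. That is fair, and power at +20 should stay in the report. Nor can one infer that power at equality is always below 80%: with a step only, marginal SD and one-sided 0.05 it is 85.0%.

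Finally, a reader might combine the end of manual screening with the statement that "Our CNN substance misuse classifier had greater than 80% sensitivity and specificity" and infer that about a fifth of existing consults would be lost, so that +20 is overstated. The documents do not support this. The sensitivity is a lower bound for classifying misuse, not a rate of lost consults. No consult-loss rate is given, and nothing says that physician referrals stop.

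**Conclusion.** The concern holds as a failure to tie the power figure to the planned test and model. It does not hold as a proven arithmetic error. The direction depends on the reading: 80% is too low for non-inferiority at a true +20 (92–100%) and for a step-only test against zero (91–97%), and too high for a test against zero with the pre-trend modelled (49–68%). For equal screens the range is 69–85% with a step only and 31–48% with trend. That step-only range contains 80%, but the plan's sentence is about +20, not equality.

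These ranges assume known autocorrelation of 0.4, 12 + 12 monthly points, one-sided alpha of 0.025 to 0.05, and both readings of the SD. This is more than missing detail: on its plain reading the figure does not use the stated margin, and the trend-adjusted analysis in the Overview does not deliver it.

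**What to change.** Replace the 80% sentence with power re-simulated for one pre-specified primary ARIMA model, stating its differencing, its orders or the selection rule, and its intervention terms. The test should be non-inferiority against −15, with power reported at true steps of 0 and +20. Report superiority at +20 separately. State alpha, sidedness, the ramp coding (0 or 1 in the first post-period month) and whether SD 10 is marginal or innovation. Report the simulated type I error beside the power, because several fits with estimated autocorrelation exceed their nominal level on 24 points.

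The cost is one simulation re-run and rewording. The price to the sponsor is a less favourable figure for a trend-adjusted superiority test and, in most of the settings above, for equal screens.
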